#### 4 STUDY POPULATION

# 4.1 Number of Subjects

Approximately 70 subjects may be enrolled.

# 4.2 Study Centers

This study will be conducted at approximately 20 sites.

#### 4.3 Inclusion Criteria

- 1. Subjects must have been treated with belumosudil for at least 1 of the following criteria:
  - Actively receiving belumosudil on Study KD025-208 or on Study KD025-213 (excluding adults in the Companion Study and excluding adolescents enrolled under KD025-213 Amendment 2 [01 June 2020])
  - b. Is in LTFU on Study KD025-208 or on KD025-213. Long-term Follow-up will be defined as the period after ending treatment with belumosudil and until an FFS event occurs.
  - c. Adult enrolled in the Companion Study under KD025-213 Amendment 2
     (01 June 2020) who has received at least 6 months of treatment of belumosudil or is in long-term follow-up
- 2. Female subjects of childbearing potential have a negative pregnancy test at enrollment. Females of childbearing potential are defined as sexually mature females without prior hysterectomy or who have had any evidence of menses in the past 12 months. However, females who have been amenorrheic for 12 or more months are still considered to be of childbearing potential if the amenorrhea is possibly due to prior chemotherapy, anti-estrogens, or ovarian suppression.
- 3. Sexually active females of childbearing potential enrolled in the study must agree to use 2 forms of accepted methods of contraception during the course of the study and for 3 months after their last dose of study drug. Effective birth control includes:
  - a. Intrauterine device plus 1 barrier method
  - Stable doses of hormonal contraception for at least 3 months (e.g., oral, injectable, implant, transdermal) plus 1 barrier method

- 2 barrier methods. Effective barrier methods are male or female condoms, diaphragms, and spermicides (creams or gels that contain a chemical to kill sperm) or
- d. A vasectomized partner
- 4. For male subjects who are sexually active and who are partners of females of childbearing potential: agreement to use 2 forms of contraception and to not donate sperm during the treatment period and for at least 3 months after the last dose of study drug.
- Subject (or the subject's legally authorized representative) is able to provide written informed consent prior to the performance of any study-specific procedures.
- 6. It is in the best interest of the subject to participate in the study.

#### 4.4 Exclusion Criteria

- 1. Female subject who is pregnant or breastfeeding
- 2. Subject considered unlikely to adhere to treatment and/or follow protocol in the opinion of the Investigator

# 4.5 Screening

No screening will be performed in this study. Subjects who meet the inclusion/exclusion criteria will be included once the ICF is signed.

#### 4.6 Withdrawal Criteria

Subjects will receive belumosudil treatment until clinically significant progression of cGVHD (defined as progression requiring addition of new systemic therapy for cGVHD), histologic recurrence of underlying malignancy, unacceptable toxicity, Investigator decision, subject preference/withdrawal of consent, loss to follow-up, Sponsor decision, or death (whichever occurs first).

Subjects who experience cGVHD progression as defined by NIH criteria but for whom no new systemic therapy is planned may continue to receive belumosudil and be assessed again at their next visit. If progression per NIH criteria is not confirmed or no new systemic therapy is planned, subjects may continue on belumosudil at the Investigator's discretion until subjects fulfill at least 1 criterion requiring discontinuation of study drug.

Belumosudil may be tapered after a sustained response for 6 months and cessation of all other immunosuppressants for at least 3 months. The tapering schedule for belumosudil is described in Dosage and Administration 5.2.

Subjects may be withdrawn from study treatment at any time by the Investigator or the Sponsor if it is considered detrimental for the subject to continue in the study. The reason for withdrawal will be captured in the eCRF.

Subjects have the right to withdraw from the study at any time and for any reason without prejudice to their future medical care by the physician or at the institution. If the subject wishes to voluntarily withdraw from the study, the physician will consult with the subject regarding procedures for safe withdrawal. Every effort should be made to have such subjects attend protocol visits including the 28-day Follow-up Visit. Reasons for withdrawal of consent will be captured in the eCRF. Subject data up to withdrawal of consent will be included in the analysis of the study, and where permitted, publicly available data can be included after withdrawal of consent.

# 4.7 Replacements

No subjects will be replaced in this study.

#### 4.8 Treatment Discontinuation

Reasons for discontinuation of treatment with belumosudil include:

- Clinically significant cGVHD progression requiring addition of systemic therapy
- Progression of underlying disease as defined by established disease specific criteria
- An AE that requires permanent discontinuation of study drug
- Investigator decision
- Voluntary discontinuation/withdrawal from study by subject (subject may remain eligible for follow-up)
- Noncompliance to protocol
- Subject lost to follow-up
- Termination of the study by Sponsor
- Subject death

#### 5 STUDY TREATMENT

# 5.1 Investigational Product

Belumosudil (2-(3-(4-(1H-indazol-5-ylamino) quinazolin-2-yl) phenoxy)-N-isopropylacetamide-methane sulfonic acid salt), previously known as KD025, is an orally available ROCK2 selective inhibitor. Belumosudil will be provided as 200 mg tablets.

# 5.2 Dosage and Administration

Subjects will be treated with the same dosage of belumosudil as they were assigned in Study KD025-208 or Study KD025-213:

- Study KD025-208: belumosudil 200 mg QD, belumosudil 200 mg BID, or belumosudil 400 mg QD
- Study KD025-213: belumosudil 200 mg QD or belumosudil 200 mg BID

Belumosudil will be tapered after a sustained response for 6 months and cessation of all other immunosuppressants for at least 3 months. Tapering is also expected if subjects withdraw for reasons other than cGVHD progression or adverse events. The tapering schedule for belumosudil is as follows:

- 200 mg QD  $\rightarrow$  200 mg QOD for 1 month $\rightarrow$  Discontinue
- 200 mg BID → 200 mg QD for 1 month → 200 mg QOD for 1 month → Discontinue
- 400 mg QD → 200 mg QD for 1 month → 200 mg QOD for 1 month → Discontinue

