# 6.4 Safety Endpoints

The follow-up safety endpoints of this study will be obtained at regular intervals and will include:

- AEs
- Grade ≥ 3 AEs
- SAEs
- Deaths
- PEs
- Vital signs
- Clinical laboratory evaluations
  - Hematologic: white blood cell count with differential, red blood cell count, hemoglobin, hematocrit, platelet count, and mean corpuscular volume
  - Serum chemistry: albumin, alkaline phosphatase, ALT, AST, blood urea nitrogen, Ca, Cl, CO2, creatinine/glomerular filtration rate (Appendix F:

Equations to Predict Glomerular Filtration Rate (MDRD-4), creatinine phosphokinase, total and direct bilirubin, gamma glutamyl transferase, globulin, glucose, lactate dehydrogenase, Mg, P, K, Na, total protein, and uric acid

 Pregnancy testing: urine pregnancy tests will be done in females of childbearing potential. Positive urine results will be confirmed with serum testing. If pregnancy is confirmed with serum testing, belumosudil will be discontinued.

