#### 7.3.5.3 Pregnancy

Pregnancies occurring in subjects enrolled in a study or in a female partner of a male study participant must be reported and followed to outcome. If a female subject inadvertently becomes pregnant while on study treatment, the subject will immediately be removed from the study. Any pregnancies of female study subjects and partners of male study subject that occur within 120 days following the last dose of study treatment must be captured in the eCRF.

The Investigator should complete the initial Pregnancy Report Form and forward it to the Sponsor (or designee) within 24 hours of becoming aware of the pregnancy as described in Section 7.3.5.1 of the protocol. If there is an associated serious outcome, then both the initial Pregnancy Report Form and SAE Report Form should be completed.

The site will follow-up with the subject at least monthly and document the subject's status until the pregnancy has been completed or terminated. The Investigator will make every effort to obtain permission to follow the outcome of the pregnancy and report the condition of the fetus or newborn to the Sponsor. The Pregnancy Report Form should be updated and submitted to the

Sponsor within 24 hours of becoming aware of the pregnancy outcome. If an SAE occurred, then the SAE Report Form must be completed and submitted as well.

In the event the pregnancy outcome occurs following the end of the study and database lock, the Investigator will report the pregnancy outcome to the Sponsor (or designee) within 24 hours after the outcome of the pregnancy is known to the Investigator in accordance with the procedure for reporting SAEs (Section 7.3.5.1).

Pregnancy alone is not regarded as an AE unless there is a possibility that the study drug may have interfered with the effectiveness of a contraceptive medication. Elective abortions without complications should not be considered AEs unless they were therapeutic abortions but should be reported to the Sponsor. Hospitalization for normal delivery of a healthy newborn should not be considered an SAE. Pregnancy is not considered an SAE unless there is an associated serious outcome. Spontaneous abortions should always be reported as SAEs.

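### Protocol 5.2 expects a 1 to 2 month belumosudil taper that by default takes in pregnancy, while 7.3.5.3 and 6.4 call for immediate removal and discontinuation

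*Protocol*

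**What the plan says.** Three parts of the protocol bear on this.

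- **Section 5.2 (Dosage and Administration)** provides a taper for sustained responders and then extends it: "Tapering is also expected if subjects withdraw for reasons other than cGVHD progression or adverse events". The schedule has one step from 200 mg QD, namely "200 mg QOD for 1 month". It has two steps from the higher daily doses, for example "200 mg BID → 200 mg QD for 1 month → 200 mg QOD for 1 month → Discontinue"; the line for 400 mg QD has the same two steps.
- **Section 7.3.5.3 (Pregnancy)** says: "If a female subject inadvertently becomes pregnant while on study treatment, the subject will immediately be removed from the study". It also settles how pregnancy is classified: "Pregnancy alone is not regarded as an AE unless there is a possibility that the study drug may have interfered with the effectiveness" (the exception concerns contraceptives).
- **Section 6.4 (Safety Endpoints)** says: "If pregnancy is confirmed with serum testing, belumosudil will be discontinued". It mentions no taper.

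The SAP does not address the point.

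**The concern.** The taper sentence works by exclusion: it covers any withdrawal that is not for one of two named reasons. Pregnancy is not cGVHD progression and, by default, is not an adverse event, so a site applying 5.2 literally would plan a taper. A site applying 7.3.5.3 and 6.4 would stop.

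At stake is a subject's exposure to study drug after a confirmed pregnancy. The protocol itself foresees the situation: it enrols females of childbearing potential (section 4.3) and tests for pregnancy at Baseline, at each 3-monthly visit and at the 28-day Follow-up Visit (Appendix A).

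**Working it through.** The check is mainly a comparison of texts. The only arithmetic is the length and quantity of the taper.

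**Step 1. Does 5.2 reach pregnancy?**

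- First exception, cGVHD progression: does not apply.
- Second exception, adverse events: by default does not apply, because 7.3.5.3 does not regard pregnancy alone as an AE. It does apply if belumosudil may have interfered with a contraceptive. In that case pregnancy can count as an AE, and 5.2 no longer expects a taper.
- Result: the default case is inside the taper sentence and the contraceptive-interference case is outside it.

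**Step 2. Can the three sections be followed together in the default case?**

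- Section 6.4 alone leaves a little room, since the schedule in 5.2 also ends in discontinuation.
- Section 7.3.5.3 removes that room. Immediate removal from the study cannot be combined with 1 or 2 more months of study dosing.
- No section ranks these instructions, and 5.2 carries no cross-reference to 6.4 or 7.3.5.3.

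**Step 3. How far apart are the readings?** Inputs: the schedule in 5.2, the 200 mg tablet in section 5.1, and an assumed 30-day month.

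- From 200 mg QD: 30 / 2 = 15 doses; 15 × 200 mg = 3,000 mg = 3 g over 1 month.
- From 200 mg BID or 400 mg QD: 30 doses in the daily month plus 15 in the alternate-day month = 45 doses; 45 × 200 mg = 9,000 mg = 9 g over 1 + 1 = 2 months.
- Under immediate discontinuation: 0 doses.
- Difference in last-dose date: about 30 days or about 60 days.

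**Step 4. Does the difference disturb the analysis?**

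- The 28-day visit (protocol 6.2.4) and the AE reporting period (protocol 6.4) are counted from the actual last dose.
- SAP 3.6 computes duration of treatment from the actual first and last dose dates.
- A later last dose moves these quantities for the subject concerned, but each rule stays well defined. Protocol 9.1 states no formal hypothesis that could be distorted.

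**The case against.** The best reply is that the pregnancy rules are specific and mandatory, while 5.2 is general and speaks only of what is expected. Most investigators would follow the specific rule. That is fair, and it is why 5.2 should not be described as directing continued drug in pregnancy. But this resolution depends on the reader; the protocol does not supply it.

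It can also be said that 5.2 concerns subjects who withdraw, whereas 7.3.5.3 concerns a subject who is removed. The distinction is thin: section 4.6 also uses withdrawal for action taken by the Investigator or the Sponsor.

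The contraceptive exception in 7.3.5.3 does narrow the conflict, and that part of the reply stands. It also makes the expectation of a taper turn on an AE classification, which is an odd basis for a dosing instruction.

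A reader might infer a wider contradiction, in which 5.2 clashes with every other stopping rule. The documents do not support that.

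- **Malignancy recurrence and withdrawal of consent.** Section 4.6 continues treatment until the first of a list that includes "histologic recurrence of underlying malignancy, unacceptable toxicity, Investigator decision, subject preference/withdrawal of consent" and, further on, a decision by the Sponsor. Several of these are the very withdrawals for which 5.2 seems to want a taper. The list can therefore be read as marking when stopping begins, with 5.2 saying how. It does not exclude a taper.
- **Recurrence as an AE.** Recurrence may also fall under the AE exception. Section 7.2 defines AEs broadly, and the KD025-213 safety summary in section 1.4.2 treats recurrent leukemia among AEs leading to death. Against this, section 4.8 lists progression of underlying disease apart from AEs. The status is unclear, which is a gap and not a contradiction.
- **Missed doses.** The discontinuation in section 5.6 after more than 7 consecutive skipped days can be waived by the medical monitor and Investigator, and the section does not say how drug is stopped.
- **Pregnancy absent from section 4.8.** That list is introduced as inclusive and contains Investigator decision, so the omission is not an error.

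**Conclusion.** The conflict over pregnancy holds. In the default case, 5.2 expects a taper of 1 month (3 g) or 2 months (9 g), while 7.3.5.3 requires immediate removal and 6.4 discontinuation, with no order of precedence. This rests on three readings: that withdrawal in 5.2 includes removal under 7.3.5.3, that the contraceptive exception does not apply, and, for the gram figures, that a month is 30 days. The figures describe what a literal taper would involve; they do not predict what sites would do. The documents give no basis for estimating how often it would arise.

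The point is one of subject safety and clear instructions. It is not a threat to the analyses, which follow actual dosing dates. Whether the taper sentence reaches recurrence of the underlying malignancy is a lesser ambiguity.

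**What to change.** Reconcile protocol sections 5.2, 6.4 and 7.3.5.3 so that they give a single instruction on study drug after a confirmed pregnancy, and make plain whether it depends on the contraceptive exception. The clinical team should decide what the instruction is; this review takes no position.

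In the same edit, 5.2 could state whether its taper sentence covers recurrence of the underlying malignancy, so that it reads clearly beside sections 4.6 and 4.8.

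The cost is about one sentence for each, by amendment or clarification letter. No data collection or SAP change follows.

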### 5.3 Treatment Assignment

Subjects will continue to receive the same dosage of belumosudil (200 mg QD, 200 mg BID, or 400 mg QD) as they were assigned in Study KD025-208 or Study KD025-213. If the Investigator reduced the dose of belumosudil in either Study KD025-208 or Study KD025-213, the subject will continue to receive that same reduced dose treatment with belumosudil through Study KD025-217 or until the AE that led to the temporary dose reduction has resolved, in which the dose treatment can resume at the original dose at the discretion of the Investigator.

# 5.4 Blinding

This will be an open-label study. No subjects will be blinded.

# 5.5 Treatment Compliance

Subjects will be given a study drug diary to record the details of each dose of study drug.

#### 5.6 Missed Doses

Subjects should make every effort to take the study drug at the same scheduled time daily with their morning/evening meal or within 5 minutes of completing the meal. In the event that the subject misses the planned dose of study drug, the protocol below should be followed:

For subjects receiving study drug on a QD dosing schedule:

- If less than 12 hours of time have elapsed after the scheduled dose, the drug should be taken. The subject should then resume the regular planned daily dosing schedule the following day.
- If more than 12 hours of time have elapsed after the scheduled dose, the drug should be skipped for that day. The subject should then resume the regular planned dosing schedule the following day.

For subjects receiving study drug on a BID dosing schedule:

- If less than 6 hours of time have elapsed after the scheduled dose, the drug should be taken. The subject should then resume the regular planned dosing schedule.
- If more than 6 hours of time have elapsed after the scheduled dose, the dose should be skipped and the subject should resume dosing with the next the regular planned dose.

If the subject skips more than 7 consecutive days of drug, the subject should be discontinued from the study unless approved by the medical monitor and Investigator.

In the event of vomiting, the subject should report the AE and should not take additional doses of study drug to compensate.

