## Disposition of Subjects

Overall, 64 subjects were screened for the study of whom 54 were included in the modified Intent-to-Treat (mITT) Population: 17 subjects in Cohort 1, 16 subjects in Cohort 2, and 21 subjects in Cohort 3. As of the cut-off date for this analysis (19 February 2020), 47 (87.0%) subjects have discontinued treatment and 7 (13.0%) subjects remain on treatment with

belumosudil. The most frequent reason for treatment discontinuation was disease progression (22 [40.7%] subjects). A total of 37 (68.5%) subjects were participating in the study, either being actively treated with belumosudil or being followed for survival (in Long-term Follow-Up). Seventeen (31.5%) subjects have discontinued from the study for the following reasons: 11 (20.4%) subjects died, 5 (9.3%) subjects were lost to follow-up, and 1 (1.9%) subject discontinued for other reasons. The overall median follow-up duration was 28.8 months: 35.9 months for Cohort 1; 32.4 months for Cohort 2; and 24.0 months for Cohort 3.

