At 3 months after Baseline and every 3 months thereafter ( $\pm$  14 days), subjects will report to the clinic for the same efficacy and safety assessments and dispensing of belumosudil at Baseline. (Height is only required at Baseline.) The study drug diaries for the past 3 months will be collected, and new study drug diaries dispensed. Any remaining belumosudil will be collected.

Subjects may receive belumosudil on Study KD025-217 for up to an additional 2 years, at the discretion of the Investigator (and with guidance from the medical monitor), beyond what they had received in Study KD025-208 or Study KD025-213, cGVHD progression, or unacceptable toxicity.

Efficacy and safety endpoints are described in Section 6.3 and Section 6.4, respectively.

Subjects will return to the clinic for a 28-day Follow-up Visit at 28 days (± 7 days) after the last dose of study drug. Subjects will have LFTU approximately every 3 months until an FFS event occurs. After the 28-day Follow-up Visit has been completed, subjects will be contacted approximately every 3 months by telephone, e-mail, or postal mail to confirm survival status, any initiation of new systemic cGVHD therapies, and relapse of underlying disease. Alternatively, this information may be obtained from the subject's medical records. The Schedule of Assessments is presented in Appendix A: Schedule of Assessments.

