# 3.2 Estimated Study Duration

Subjects may receive belumosudil for 2 years at the discretion of the Investigator and with guidance from the medical monitor.

Subjects will be treated with belumosudil until cGVHD progression or unacceptable toxicity.

Subjects will return to the clinic for a 28-day Follow-up Visit (± 7 days) after the last dose of study drug. Subjects will have long-term follow-up approximately every 3 months until an FFS event occurs. After the 28-day Follow-up Visit has been completed, subjects will be contacted approximately every 3 months by telephone, e-mail, or postal mail to confirm survival status, any initiation of new systemic cGVHD therapies, and relapse of underlying disease (see Section 3.1). Alternatively, this information may be obtained from the subject's medical records.

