### 5.10 Dose Modification Guidelines

Any clinically significant toxicity will necessitate consideration of either a pause or cessation of therapy. Guidelines for management of treatment-emergent toxicities in subjects receiving belumosudil are outlined in Table 5. When dose reduction is necessary, the dose should be decreased as shown in Table 6.

Table 5. Guidelines for the Management of TEAEs with Belumosudil Treatment

Toxicity	Recommended Action		
Grade 4 organ toxicities considered at least possibly related to belumosudil	Discontinue belumosudil		
Grade ≥ 3 LFTs (AST, ALT or total bilirubin) regardless of attribution to belumosudil	
 
Hold belumosudil dosing until resolution to Grade 1 or below levels
 
Consider resuming belumosudil. If resuming, then resume at 1 dose decrement
 
If toxicity recurs, discontinue belumosudil
 
		
Other Grade ≥3 clinically significant toxicities considered at least possibly related to belumosudil	Hold belumosudil dosing until toxicity has resolved to Grade 1 or below then consider resuming belumosudil. If resuming, then resume at 1 dose decrement     If toxicity recurs, hold dose as above then consider resuming belumosudil at one dose decrement		

ALT = alanine aminotransferase; AST = aspartate aminotransferase; eCRF = electronic case report form; LFT = liver function test; TEAE = treatment-emergent adverse event

Dose interruption for up to 14 days for toxicity management is permitted. Subjects requiring pauses of more than 14 days will be discontinued from the study unless approved by the medical monitor.

Table 6. Belumosudil Dose Decrements

Belumosudil Dose	Dose Reduction	
400 mg QD	200 mg QD	
200 mg BID	200 mg QD	
200 mg QD	200 mg QOD	

BID = twice daily; QD = once daily; QOD = once every other day

If the reduced dose of belumosudil is tolerated for 1 month, the dose may be escalated to the previous dose.

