### 6.2.5 Long-term Follow-up

Long-term Follow-up will start at Baseline for enrolled subjects who have been permanently discontinued from belumosudil in Study KD025-208 or in Study KD025-213 where they have not yet had an FFS event. The LTFU will occur after the 28-day Follow-up Visit has been completed for enrolled subjects who were actively dosed with belumosudil at Baseline.

Subjects will have LTFU approximately every 3 months until an FFS event occurs. This LTFU assessment will occur by subjects being contacted by telephone, e-mail, or postal mail to confirm survival status, any initiation of new systemic cGVHD therapies, and relapse of underlying disease. Alternatively, this information may be obtained from the subject's medical records.

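### Protocol 5.6 and 5.10 take subjects with long dosing gaps off the study, while 3.1, 3.2 and 6.2.5 require them to be followed until an FFS event

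*Protocol*

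**What the plan says.** Two rules in Protocol Section 5 attach study discontinuation to a dosing gap.

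- **5.6 Missed Doses:** a subject who "skips more than 7 consecutive days of drug, the subject should be discontinued from the study unless approved by the medical monitor and Investigator".
- **5.10 Dose Modification Guidelines:** "Subjects requiring pauses of more than 14 days will be discontinued from the study unless approved by the medical monitor".

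Three sections describe follow-up after the last dose.

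- **3.1 Study Design:** a 28-day visit after the last dose, and "Subjects will have LFTU approximately every 3 months until an FFS event occurs".
- **3.2 Estimated Study Duration:** "Subjects will have long-term follow-up approximately every 3 months until an FFS event occurs".
- **6.2.5 Long-term Follow-up:** "The LTFU will occur after the 28-day Follow-up Visit has been completed for enrolled subjects who were actively dosed with belumosudil at Baseline".

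None of these three sections makes an exception for subjects stopped because of a dosing gap. Inclusion criterion 1b (4.3) defines LTFU as running from the end of belumosudil until an FFS event.

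**The concern.** Read literally, 5.6 and 5.10 end study participation at the point where 3.1, 3.2 and 6.2.5 start follow-up. Sites would have to choose between the two instructions.

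The study's only objective is long-term safety and efficacy. SAP 3.7.2.3 to 3.7.2.5 censor time to next treatment (TTNT), FFS and overall survival (OS) at the latest available response or LTFU assessment. The tertiary definition of duration of response (SAP 3.7.2.1, Table 2) is censored in the same way. A subject removed after a toxicity pause or a run of missed doses would be censored early, for a reason that may be related to outcome. The 28-day safety visit could be lost as well.

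**Working it through.** The documents give no figure to reproduce on this point, so the check is a comparison of the text.

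**1. Do the triggers coincide with an FFS event?** SAP 3.7.2.4 counts three components: new systemic cGVHD therapy, non-relapse mortality and recurrent malignancy. Neither a gap of more than 7 days nor a pause of more than 14 days is among them. A subject who stops for a gap has therefore not reached the end of LTFU as 3.1, 3.2 and 6.2.5 define it.

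**2. Does the protocol treat leaving treatment and leaving the study as different events?** It does.

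- Section 4.6 uses both terms in successive paragraphs: "Subjects may be withdrawn from study treatment at any time by the Investigator or the Sponsor", then "Subjects have the right to withdraw from the study at any time and for any reason".
- Section 15.4 asks for dates and reasons for either event.
- The parent-study disposition in 1.4.1 and 1.4.2 counts them separately. For KD025-208 it states that "Seventeen (31.5%) subjects have discontinued from the study".

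| Parent study | Treated | Off treatment | Off study | Off treatment but still in study |
|---|---|---|---|---|
| KD025-208 | 54 | 47 | 17 | 47 − 17 = 30 |
| KD025-213 | 132 | 62 | 13 | 62 − 13 = 49 |

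The last column agrees with the stated totals still participating: 30 + 7 on treatment = 37, and 49 + 70 on treatment = 119. So leaving the study has a distinct meaning in this document, and a site could reasonably apply it.

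**3. Can the trigger arise when a site follows the protocol?** Table 5 in 5.10 holds belumosudil until toxicity falls to Grade 1 or below. This applies to Grade 3 or higher liver tests whatever the attribution, and to other clinically significant Grade 3 or higher toxicities considered at least possibly related. The table puts no time limit on the hold, so a hold that complies with it can pass 14 days.

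**4. Does any section say that these two sentences mean treatment only?** None does.

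**5. How many subjects would be affected?** The documents give no interruption lengths, no waiver rate, no count of skipped-dose gaps and no split of enrollees between active treatment and LTFU. Only actively treated subjects are exposed to the rules. For context, in KD025-213 the number with a treatment-emergent adverse event leading to dose interruption was 19 + 16 = 35, and 35/132 = 26.5%. These interruptions were of any length. The figure shows that interruptions occur; it does not estimate how many exceed 14 days, and it is not a forecast for KD025-217.

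**The case against.** The strongest reply is that this is loose wording which the rest of the protocol points towards resolving.

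- Section 4.8 lists noncompliance, and adverse events requiring permanent discontinuation of drug, as reasons to stop treatment. These are close counterparts of 5.6 and 5.10. It also allows for follow-up after voluntary withdrawal.
- Table 5 asks only for belumosudil to be stopped after a related Grade 4 organ toxicity. It would be odd for a 15-day pause to have a harsher consequence.
- Section 4.6 asks for every effort to bring subjects who voluntarily withdraw to protocol visits, including the 28-day visit. Section 7.3.5.3 removes a pregnant subject from the study yet follows her at least monthly. Section 7.4.2 follows adverse events to resolution or stability.
- The parent-study counts are not rules of this study, and none of the reasons they list for leaving the study is a dosing gap.
- Harm needs a gap over the threshold, no waiver, a literal reading, and no retrieval of status from medical records, which 6.2.5 permits. Section 5.6 also says should rather than will.
- LTFU already ends at any FFS event, so survival after new therapy or relapse is not followed in any case.
- In KD025-213 the median relative dose intensity was 99.7%, and 110 of 132 subjects (83.3%) were above 95%, which suggests that long gaps were uncommon.

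Most of this stands as evidence of intent and of limited impact. It does not remove the conflict. The follow-up clause in 4.8 is attached to voluntary withdrawal only. Section 7.3.5.3 spells out its follow-up, whereas 5.6 and 5.10 do not. Section 7.4.2 concerns adverse-event outcomes, not survival, new therapy or relapse. The dose-intensity figures are not defined in a way that bounds gap length. If treatment discontinuation was intended, these two sentences state something else.

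**Conclusion.** The point holds. As written, and absent a waiver, 5.6 and 5.10 cannot be reconciled with 3.1, 3.2 and 6.2.5. The likely explanation is a wording error, and loss of follow-up is a risk rather than a certainty.

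The size of the effect cannot be estimated from the documents, either as a number of subjects or as bias. It is limited in kind. TTNT, FFS and OS are descriptive secondary endpoints, Protocol 9.1 sets no formal hypothesis, and the overall response rate does not use LTFU contacts. The conclusion that censoring could be informative assumes that a site applies the literal wording, that no waiver is given, and that the reason for the gap is related to outcome. The point ranks as a free improvement.

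**What to change.** In Protocol 5.6 and 5.10, replace the instruction to discontinue the subject from the study with: discontinued from study treatment, complete the 28-day Follow-up Visit and continue in LTFU until an FFS event (Section 6.2.5). Keep both waivers as they are: medical monitor and Investigator in 5.6, medical monitor in 5.10.

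The cost is the wording of two sentences. The 28-day visit (6.2.4) and the LTFU contacts (6.2.5) are already planned, so no procedure is added. If sites already work this way, the edit only records it.
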